## 2. Methods.

- I. **Research participants.** We will recruit and enroll 40 women early in pregnancy (< 20 weeks gestation) from the University of Illinois at Chicago (UIC) Obstetrics (OB) clinics located at the University of Illinois Hospital and Health Sciences System (UIHHSS) Outpatient Care Center, Center for Women’s Health. Women will be between the ages of 18 – 45 years old and at risk for maternal ID based on hemoglobin of 10.0 – 11.9 g/dl assessed as part of standard clinical care during the first prenatal OB visit.
- II. **Eligibility, recruitment, and informed consent:** After obtaining a waiver of consent for recruitment purposes, we will complete a pre-screen eligibility checklist of women < 20 weeks gestation who are seeking prenatal care at the UIC Obstetrics Clinics at the UIHHSS Center for Women’s Health. Potentially eligible women will be identified through clinic schedules and eligibility assessed via Cerner/EHR (only if data is available, data will not be available for new UIC patients). Women identified as potentially eligible through the EHR data or new UIC patients attending their first OB prenatal appointment will be approached in clinic. A research team member will introduce the study, assess interest, and further determine eligibility using a screening checklist. Interested and eligible women will be asked to provide contact information. As part of routine care, maternal hemoglobin will be assessed following the first OB visit. For women that express interest in the study and provide contact information, hemoglobin results will be followed up in Cerner. Women will be called regardless of their results to report on continued study eligibility. If hemoglobin is within the study defined range (10.0 – 11.9 g/dl) women will be invited to participate. Those who continue to express interest will be asked to schedule a baseline appointment at the UIC Clinical Research Center (CRC)s. Women will be consented at the baseline visit. Research personnel will explain to every eligible woman that their choice to participate will in no way affect their standard of care at UIHHS.

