### III. Inclusion/exclusion criteria.

- a. Inclusion criteria: obtaining prenatal care at UIC; initial prenatal hemoglobin between 10.0 – 11.9 g/dl; 18 - 45 years of age; spontaneous/natural conception; singleton pregnancy; < 20 weeks gestation; and willing to: a) fast for at least 2 hours prior to research data collection visits (3 occasions), b) agree to randomization; c) ingest Lp299v + standard PNVI or standard PNVI + placebo daily through delivery; c) refrain from **ALL** other supplements including other PNVs unless medically indicated (e.g., folate); d) attend 3 research data collection visits at UIC; e) undergo 3 venipunctures; and f) come to UIC on 4-5 occasions (separate from research visit but will be coordinated around standard clinical care visits) to pick up supplements and have study compliance monitored/checked. Women will also be able to read and write English, and have access to a smart phone. Also, women must agree to refrain from **ALL** other pre and probiotic supplements (unless medically indicated) including Activia yogurt, Kefir, Tropicana Probiotic, and Good Belly products while in the study.
- b. Exclusion criteria: Autoimmune disorder; current or previous premature rupture of membranes or clinical chorioamnionitis; current bacterial or viral infection; oral antibiotic use in the last 3 months; receiving steroid or anti-inflammatory treatment; previous bariatric surgery; malabsorptive condition; current hyperemesis; hematologic disorder (i.e., sickle cell disease or hemochromatosis); current tobacco use or within the past 1 month; current alcohol consumption; current drug use; or type 1 or 2 diabetes given these factors may influence the biological markers.

**IV. Randomization.** Women will be randomized to the Lp229V + standard PNVI or standard PNVI + placebo following the baseline visit.

**V. Treatment groups.** Women will be assigned to one of two treatment groups as described below.

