22. Generalized Anxiety Disorder 7-item (GAD-7) Scale. This is a 7-item scale that measures anxiety.
23. IDAS-II III Temper (Anger) Scale. This is a 5-item scale that measures anger.
24. Intolerance of Uncertainty Scale – Short Form. This is a 12-item scale that measures intolerance of uncertainty.
25. Pittsburgh Sleep Quality Index. This is a 24-item scale that measures sleep.

Hair collection: If the woman agrees, a sample of hair (70-100 strands) will be collected from the crown of her head (about 70-100 strands) by trained research staff.

Rectal Swab: If the woman agrees, using the kit provided, she will collect two rectal swabs.

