7. Adult violence exposure. This is a 29-item survey used to identify exposure to violence of the past 7 days. The survey is used to classify low- and high-violence exposure that has demonstrated good construct validity, internal consistency, test-retest reliability, and validity.
8. Social support – MOS social support survey. This survey was designed to be comprehensive in terms of recent thinking about the various dimensions of social support.
9. Healthy Pregnancy Stress Scale. This is an 18-item scale that measures pregnancy stressors women have experienced during their pregnancy.
10. Hair collection survey. This survey was developed by the research team and asks about hair care practices.
11. Short Scale Anxiety Sensitivity Index (SSASI). This is 5-item scale that measures anxiety.
12. Behavioral Inhibition System & Behavioral Activation System Scales. This is a 24-item scale that measures behavioral inhibition and activation.
13. Brief Irritability Test (BITe). This is a 5-item scale that measures irritability.
14. Generalized Anxiety Disorder 7-item (GAD-7) Scale. This is a 7-item scale that measures anxiety.
15. IDAS-II III Temper (Anger) Scale. This is a 5-item scale that measures anger.
16. Intolerance of Uncertainty Scale – Short Form. This is a 12-item scale that measures intolerance of uncertainty.
17. Pittsburgh Sleep Quality Index. This is a 24-item scale that measures sleep.

Hair collection (34-36 weeks only): If the woman agrees, a sample of hair will be collected from the crown of her head (70-100 strands) by trained research staff.

Rectal Swab (baseline, 24-28 and 34-36 weeks): If the woman agrees, using the kit provided, she will collect two rectal swabs.

Maternal health data: We will abstract from the EHR data pertaining to recent illness or infection, new medications, and change in health status (i.e., development of a pregnancy related condition like gestational diabetes).

Pill pick up and adherence monitoring (24-28 weeks and 34-36 weeks gestation):

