We will monitor adherence using electronic pill monitoring technology Pillsy and standard pill counts. Women will get a new 30-40-day allotment of pills. During these visits, we will download data from the Pillsy app on their smart phones and conduct a physical pill count. If a woman is found to be non-compliant (i.e., consuming <75% of pills) with her permission, she will receive automated daily text messages around dinner time to help increase compliance with the supplement interventions.

**Pill pick up and adherence monitoring visits (approximately @ 18-19 weeks, 22-23 weeks, 30-31 weeks, 38-39 weeks).** We will monitor adherence using electronic pill monitoring technology Pillsy and standard pill counts. Women will visit UIC approximately every 28 days to get a new 30-40-day allotment of pills and for compliance to be assessed. If possible, these encounters will be coordinated around standard clinical prenatal care appointments. If not, separate pill pick up visits and under certain conditions home pill drop-off will be coordinated. During these visits, we will download data from the Pillsy app on their smart phones and conduct a physical pill count. If a woman is found to be non-compliant (i.e., consuming < 75% of pills) with her permission, she will receive automated daily text messages around dinner time to help increase compliance with the supplement interventions. We will administer the GI symptoms checklist at each visit.

- c. Feasibility and Tolerability. Feasibility will be based on accrual and withdrawal/loss to follow-up rates at the end of the study and adherence determined using the Pillsy smart bottles and standard pill counts. The intervention will be considered feasible if 50% of women approached for participation enroll, overall withdrawal rate is  $\leq 15\%$  and adherence to the supplement regimen is  $\geq 85\%$ . Tolerability [(potential adverse events (AEs) (e.g., GI symptoms)] will be assessed via phone/email/text using the Pillsy app weekly for the first 4 weeks and bi-weekly thereafter. The intervention will be deemed tolerable if no serious AEs (highly unlikely) are documented, and the rate of non-serious AEs is similar between study arms.

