## **XII. Data management.**

Research staff will enter all data directly into a Research Electronic Data Capture (RedCap) (Vanderbilt University, Nashville, TN) data structure. Standard checks for outliers, duplicates, and other errors associated with data entry will be conducted. Dietary data will be collected using the online Diet History Questionnaire-II (NCI, Bethesda, MD).

**XIII. Statistical analysis.** Statistical analysis will be performed using SAS (v. 9.4., Cary, NC). Variables not normally distributed will be transformed and if normality not achieved, non-parametric tests will be utilized. Data that are left censored due to undetectable levels will be analyzed using imputation or tobit regression to avoid biased estimates. Descriptive statistics including means, medians and standard deviations for continuous variables and frequency for categorical variables will be used to describe the women, serum, and rectal swabs outcomes at baseline. Differences between treatment groups (Lp299v + standard PNVI vs. standard PNVI + placebo) for the baseline variables will be compared by t-test or non-parametric equivalent with Bonferroni correction and categorical data via chi-square or Fisher exact test. The correlation between the continuous variables at each time-point, baseline, 20 – 24, 34 – 36 and delivery overall and within each group will be assessed by Spearman or Pearson correlation coefficients. A two-way analysis of variance, using a general linear model for repeated measures between treatment groups and time-points will be examined. If significant effects are observed over time, single different pregnancy time-points (i.e., 24 - 28, 34 - 36 gestational week) will be tested. All *P* values were based on a two-sided test of statistical significance accepted at the level of  $P < 0.05$ .

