The rectal swabs microbial 16s rRNA sequencing data will be analyzed with QIIME and PICRUSt. Baseline microbial abundance, diversity, and predicted microbial metabolisms will be assessed. For feasibility, # of charts screened, prescreening eligible, approached, and enrolled will be calculated. The # of visits completed at each time point and end of study attrition will be determined and differences between groups calculated. Adherence (# of pills consumed) and # of SAEs/AEs will be calculated and compared between groups. Maternal stress response, maternal iron-related parameters, and inflammation at baseline, 24-28 weeks, 34-36 weeks and labor and delivery, will be evaluated using repeated measures ANOVA and ANCOVA to adjust for baseline differences. Infant iron status at delivery will be compared between groups (Student's t-test). Microbial abundance, diversity and microbial metabolisms will be compared between groups at baseline, 24-28 weeks, 34-36 weeks (Student's t-test/Mann Whitney U) and within group changes at 24-28 weeks and 34-36 weeks will be determined. The mediating effects of maternal rectal swabs microbiome, systemic inflammation and iron regulatory responses on the relationship between Lp299v on maternal stress- and iron-related outcomes will be explored using generalized linear models. Multiple comparisons and false discovery rate adjustments will be used accordingly.

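### The named between-arm tests of the swab outcomes do not adjust for the baseline swab: they are valid but can be inefficient, and the plan does not say which analysis governs these outcomes

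*Combined protocol and SAP*

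**What the plan says.** Specific Aim 2 carries a between-arm hypothesis: more Lp299v colonization and propagation in the probiotic arm at the two follow-up visits. Swabs are requested at baseline and at both follow-up visits, and they are voluntary: "If the woman agrees, using the kit provided, she will collect two rectal swabs".

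Three statements in section XIII bear on the analysis.

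- The only sentence that assigns a between-arm method to the microbial outcomes reads "Microbial abundance, diversity and microbial metabolisms will be compared between groups at baseline, 24-28 weeks, 34-36 weeks", with Student's t-test or Mann-Whitney U in parentheses. It continues "within group changes at 24-28 weeks and 34-36 weeks will be determined". It names no baseline covariate and no between-arm test of change.
- Earlier in that paragraph, repeated measures ANOVA and baseline-adjusting ANCOVA are assigned to maternal stress response, iron parameters and inflammation. Swab outcomes are not in that list.
- The preceding paragraph plans a two-way repeated-measures general linear model across treatment group and time-point, with single time-points tested afterwards if an effect over time is seen. It does not name the outcomes it covers.

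The trial size is given as "We will recruit and enroll 40 women early in pregnancy (< 20 weeks gestation"), and no power calculation accompanies it.

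**The concern.** A pre-treatment measurement of the same outcome is usually among the more useful covariates available. Here it is collected, and the authors plan to use such a measurement for the blood and stress markers, yet the named between-arm swab test leaves it out. In a trial of at most 40 women, with voluntary swabs, that could mean a wider confidence interval and a missed difference.

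There are two secondary issues. Within-arm change is the only analysis of change that the plan names for swabs, and it is not labelled descriptive, so a report could set a change in one arm against no change in the other. And if the general group-by-time model was also meant for swabs, Aim 2 has two analyses with no rule for which one is reported as the result.

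**Working it through.** **Inputs from the protocol.** Total of 40 women (section 2.I). Significance is by "two-sided test of statistical significance accepted at the level of" 0.05 (section XIII). Feasibility is defined by a withdrawal rate of at most 15% (section VI, Feasibility and Tolerability), so 40 × 0.85 = 34 women is used as a lower case.

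**Assumptions.** Section IV says "Women will be randomized to the Lp229V + standard PNVI or standard PNVI + placebo following the baseline visit" and gives no ratio, so 1:1 is assumed: 20 per arm, or 17 per arm in the lower case. The protocol gives no effect size, SD or baseline-to-follow-up correlation r. A 0.8 SD difference is used for illustration, with r from 0 to 0.7. Each calculation is for one outcome, one visit and one test at 0.05. There is no power figure in the plan to reproduce.

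**Step 1: variance.** With equal SDs at the two visits, the variance of the between-arm difference, relative to the follow-up-only test, is 1 − r² for ANCOVA and 2(1 − r) for a comparison of change from baseline.

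| r | Follow-up only | Change from baseline | ANCOVA | Women a follow-up-only test needs to match ANCOVA in 40: 40/(1 − r²) |
|---|---|---|---|---|
| 0 | 1.00 | 2.00 | 1.00 | 40.0 |
| 0.3 | 1.00 | 1.40 | 0.91 | 44.0 |
| 0.5 | 1.00 | 1.00 | 0.75 | 53.3 |
| 0.7 | 1.00 | 0.60 | 0.51 | 78.4 |

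**Step 2: power (noncentral t).** Unadjusted: noncentrality = d / √(2/n), with 2n − 2 df. For n = 20: 0.8 / √0.1 = 2.53 on 38 df, giving 69.3%. Adjusted: divide the noncentrality by √(1 − r²), with 2n − 3 df. For r = 0.5: 2.53 / 0.866 = 2.92 on 37 df, giving 81.2%.

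| n per arm | Unadjusted | Adjusted, r = 0 | r = 0.3 | r = 0.5 | r = 0.7 |
|---|---|---|---|---|---|
| 20 | 69.3% | 69.3% | 73.3% | 81.2% | 93.2% |
| 17 | 61.9% | 61.8% | 65.9% | 74.2% | 88.6% |

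At 20 per arm the gain is nil at r = 0, about 4 points at r = 0.3, about 12 at r = 0.5 and about 24 at r = 0.7. Adjusting for a useless baseline costs essentially nothing (one degree of freedom).

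**Step 3: validity and within-arm tests.** Simulation used 20,000 trials per setting, 20 per arm, r = 0.5 and no true arm difference. The planned between-arm t-test rejected in about 5% of trials, as it should. Paired t-tests run separately in each arm were significant in exactly one arm in about 9% of trials with no time shift, 38% with a common shift of 0.3 SD, and 49% with a common shift of 0.5 SD. The no-shift figure agrees with 2 × 0.05 × 0.95 = 9.5%. The protocol gives no size for any shift with gestation.

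**The case against.** The strongest reply is that the plan already uses the baseline swab. Within-arm changes use it. The general group-by-time model could be read as covering swabs too: its paragraph mentions swab outcomes, and the example time-points it would test singly are exactly the swab follow-up visits. On that reading the t-tests are only the second step. A reader might therefore infer that the plan ignores each woman's baseline swab altogether, and the documents do not support so absolute a statement. What stands is narrower. The model names no outcomes, while the sentence that does name the microbial outcomes specifies an unadjusted test. Nor would the model settle the efficiency question: a group-by-time contrast between baseline and one follow-up visit compares change scores, which are less precise than the follow-up-only test when r is below 0.5 and less precise than ANCOVA throughout the range shown.

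A reader might also infer that the arms will be judged by within-arm significance, or that the planned test is biased. Neither is supported. A direct between-arm test is specified and holds its error rate under randomization, and the plan promises no within-arm P values. The percentages in step 3 are a reason to label the within-arm results, not evidence of a planned error.

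Other parts of the reply also stand. Aim 2 concerns Lp299v itself; if its level before treatment is near floor, which is plausible but not stated, baseline adjustment gains little for that endpoint. Optional swabs do not prove that fewer than 40 women will contribute; the number is at most 40 and may be lower. The plan also promises multiplicity and false discovery rate adjustment, which would lower every power figure above. Finally, plain ANCOVA drops women without a baseline swab, whom the planned follow-up tests would keep, so the fix must deal with them.

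**Conclusion.** The point holds as an inexpensive improvement in efficiency and clarity, not as a defect in validity. The between-arm comparison named for microbial abundance, diversity and metabolisms leaves out a baseline measurement that the trial collects, and the plan does not say whether the general repeated-measures model applies to these outcomes.

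Under the stated assumptions, adjustment moves power from about 69% to between 69% (r = 0) and 93% (r = 0.7). The correlation is unknown, so the true gain may lie anywhere in that range. It is likelier to matter for the diversity and general abundance outcomes than for Lp299v itself.

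**What to change.** In the microbial sentence of section XIII:

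1. Make the between-arm comparison at 24-28 and 34-36 weeks a baseline-adjusted model for each outcome: ANCOVA on suitably transformed or ranked values, or a mixed model of all three visits with the baseline mean constrained equal across arms. The mixed model keeps women who lack a baseline swab.
2. Report the adjusted between-arm difference with its 95% CI at each follow-up visit.
3. State that within-group changes are descriptive and are not evidence of a difference between arms.
4. State that this analysis, and not the general group-by-time model in the preceding paragraph, governs the swab outcomes.

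The cost is a few lines of text and slightly more modelling work. No further data need be collected. Zero-heavy features, possibly including Lp299v at baseline, need care: a rank-based version should be named for them in advance, with the expectation that adjustment may change little there.

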#### **XIV. Data and safety monitoring plan.**

The PI will establish a data safety monitoring plan and follow all procedures for the protection of human subjects as required by UIC. The purpose of this data and safety monitoring plan is: (1) to ensure the safety of study subjects and the validity of data; and (2) to produce high quality research while considering both risks and benefits. The PI and research assistants will meet weekly to monitor the components of the research study.

Assessment of study risk. The probiotic proposed for use in the study is not contraindicated during pregnancy and therefore has not been shown to pose any adverse risk to the pregnant woman or her fetus. All other study procedures, based on UIC guidelines should be determined as minimal risk.

Data monitoring plan. The PI will monitor the following items: data quality, completeness, and timeliness; adequacy of compliance with goals for recruitment and retention, including those related to participation of minorities; adherence to the protocol; and adverse events reported by subjects at study and adherence visits. If an adverse event is reported during the study, subjects will be requested to report the event to their physician and the PI. All adverse events will be documented and reported to the UIC IRB in a timely manner based on the type of adverse event (adverse event vs. serious adverse event). We will also record and track reasons for dropout. All authorized study personnel will be required to notify the PI of any unanticipated problems/adverse events immediately upon discovery. The PIs will immediately notify the UIC IRB. The study will be subject to annual review and recertification by the OPRS.

Experimental Aim 2: The Maternal Stress Reduction Project, "Happy Moms" Focus Groups  
Information collected from the focus groups will help inform the development of a curriculum focusing on lifestyle and dietary approaches to reduce chronic stress from structural violence. The curriculum will be developed into a series of classes that will be offered at the New Moms Austin Chicago location. The classes will be open to focus group participants and women currently participating in Family Support programs offered by New Moms.

The Maternal Stress Reduction Project, "Happy Moms": Recruitment, Eligibility, Informed Consent and Data Collection

Recruitment: will be conducted via informational handout by members of the New Moms staff or members of the research team. New Moms offers both in-home and onsite programming for their clients. During these programs, members of the New Moms staff or a member of the research team will inform their clients about the opportunity to participate in a focus group centered around healthy diet and lifestyle choices. Interested individuals will be provided with a copy of the "Informational Handout" and instructed to contact the study number on the handout for more information or to enroll. We will recruit up to 24 women, between the age of 18-45 that are currently attending New Moms Family Support programming. Recruitment of participants will take place during New Moms Family Support programming via Informational Handout by a member of the

research study staff or a New Moms staff member. During the class sessions, a study staff member or New Moms staff member will distribute the Informational Handout informing Family Support programming participants about the opportunity to participate in a research study. Interested individuals will be directed to contact the study number on the Informational Handout for more information or to enroll. Interested individuals that contact the study number will receive a call from a member of the research staff in a semi-private space in the Westside Research Office Building to determine eligibility and explain focus group activities. Only members of the research staff and focus group participants for that session will be aware of a participant's status as a research participant.

**Eligibility:** A member of the study staff will return the call of a potential participant that leaves a message on the study number voicemail. When returning the call, the study staff member will follow the "Phone Script" to explain that the project is a research study and to describe the study purpose and activities to the potential participant. During the call, eligibility will be determined by asking the potential participant if they currently attend New Moms Family Support programs. If yes, they will be invited to participate in a focus group session and offered one of two focus group dates. The potential participant will choose the date that best fits their schedule. Once a date is selected, the potential participant will be provided with a location and time. No additional information will be collected from the participant at this time. All focus groups will be conducted at New Moms Austin location in Chicago.

**Informed Consent:** will be conducted at the beginning of the focus group session. A member of the study staff will review each section of the consent form with the focus group members as a group. The focus group attendees will be given the opportunity to ask questions and be reminded that their participation in the study is completely voluntary and that they can discontinue participation at any time. Individuals that choose to participate in the focus group will be asked to sign and date two copies of the consent form (one to keep and one to be given to study staff). Study staff will also sign and date both copies of the consent form at that time. Those that choose not to participate will be thanked for their time and asked to leave the focus group session before it begins.

**Data Collection:** Once all participants are consented, the brief demographic questionnaire will be distributed. When all questionnaires are completed, a member of the study staff will collect the questionnaire and begin the focus group session. Participants will be asked about their barriers and challenges to a healthy diet and lifestyle. The focus group sessions will be audio recorded to allow research staff to capture the discussion in full. During the focus group session participants will use first names only. All name tags will be collected at the end of the focus group session. For the Maternal Stress Reduction Project, "Happy Moms", a 1-2-hour focus group session. We are audio recording the focus group sessions for immediate download onto a laptop with TruCrypt software. The focus group session audio recordings will not be stored on the audio recording device. The audio recordings will be transferred to the laptop with TruCrypt immediately following the focus group session and deleted from the audio recording device. All focus group participants will be asked not to discuss the focus group session or its participants with anyone not in the focus group session. During the focus group, participants will be issued name tags with only their first names that will be collected at the end of the session.

**Data Analysis:** All qualitative data will be analyzed using qualitative analysis software (ATLAS.ti). We will identify emergent themes about experiences using the team consensus codes. Codes will be developed and discussed in team meetings to enhance consistency in application. Final codes will be compiled in the master codebook and applied to the coding of all qualitative data. The data will be double-coded; after coding separately, the 2 coders will consult with the team to review discrepancies, refine code definitions and recode until intercoder reliability exceeds 85%. The most common themes will be used to inform the intervention. For example, if a top common theme is fast-food consumption as a means to reduce stress, this would be targeted in the future intervention/curriculum.

